### **CMT-HI**

Individual CMT-HI scored data (total score and each of the subscale scores) will be listed.

Descriptive statistics for the total CMT-HI score as well as for each subscale score will be provided by treatment group and scheduled time for raw data and absolute change from baseline. A line graph of the mean  $\pm$  SEM will also be provided for the absolute change from baseline by treatment for each scheduled time.

Least square mean estimates of the effect of ACE-083 and corresponding 90% and 95% confidence intervals will be produced for the Day 190 absolute change data described above using an ANCOVA model with BASELINE, CMT-TYPE, and TREATMENT as covariates

where BASELINE, CMT-TYPE, and TREATMENT are defined similarly as described above for other analyses.

Similar analyses will be done for each of the individual subscale scores.

In addition, a bar chart of the Day 190 least squares mean absolute change estimates ( $\pm$  SEM) will be provided for the following CMT-HI parameters: CMT-HI total score, CMT-HI mobility, CMT-HI activities, CMT-HI pain, and CMT-HI balance.

If the Day 190 CMT-HI has no missing data, then the above ANCOVA model will be used for analysis. If missing data is present, a standard multiple imputation with the above ANCOVA model will be used for analysis as described in [Section 4.11.1](#).

A mixed model repeated measures (MMRM) analysis will be performed to assess the sensitivity to the ANCOVA analyses described above. An unstructured covariance structure will be used to model the within-patient covariance across visits. Other covariance structures will be considered if the unstructured covariance fails. The covariates to be included consist of all of the covariates described above for the ANCOVA with the addition of the following additional covariates: VISIT where VISIT represents the scheduled visit day post first dose of MRI assessment and TREATMENT\*VISIT.

Similar to what was described for the ANCOVA analysis above, if missing data is present, a standard multiple imputation with the above MMRM model will be used for analysis as described in [Section 4.11.1](#).

The findings from the ANCOVA model described above will be considered primary.

Additional analyses may be performed as appropriate.

## **CMTES2**

Individual data will be listed.

Descriptive statistics for the CMTES2 score will be provided by treatment group for raw data and changes from baseline (absolute and percent change). In addition, a line graph of the mean  $\pm$  SEM will also be provided for the absolute change from baseline by treatment for each scheduled time.

Least square mean estimates of the effect of ACE-083 and corresponding 90% and 95% confidence intervals will be produced for the Day 190 absolute change data described above using an ANCOVA model with CMT-TYPE, BASELINE, and TREATMENT as covariates where BASELINE refers to the baseline CMTES2 score and CMT-TYPE and TREATMENT are defined similarly as described above for other analyses. In addition, a bar chart of the least squares mean estimates ( $\pm$  SEM) for each treatment group will be provided.

If the Day 190 CMTES2 assessment has no missing data, then the above ANCOVA model will be used for analysis. If missing data is present, a standard multiple imputation with the above ANCOVA model will be used for analysis as described in [Section 4.11.1](#).

The statistical analyses described above will be done on the Per Protocol Set and will be considered primary. The analyses described above will also be repeated for the Full Analysis Set.

Additional analyses may be performed as appropriate.

### **Gait**

Individual data will be listed.

Descriptive statistics of the raw data and change from baseline (percent and absolute change) will be provided for each type of measurement recorded (i.e. “General measures”, “Gait cycle phase measures”, “Gait assessment range of motion”, and “Gait assessment foot drop”) by cohort and scheduled time (for Part 1) and by treatment group and scheduled time (for Part 2).

Descriptive statistics for the average absolute and average percent change from baseline for the left and right sides will also be provided.

Least square mean estimates of the effect of ACE-083 and corresponding 90% and 95% confidence intervals will be produced for the Day 190 average absolute change from baseline for the left and right sides for the mid-swing foot angle using an ANCOVA model with CMT-TYPE, BASELINE, and TREATMENT as covariates where BASELINE refers to the baseline average mid-swing foot angle for the left and right sides and CMT-TYPE and TREATMENT are defined similarly as described above for other analyses. In addition, a bar chart of the least squares mean estimates ( $\pm$  SEM) for each treatment group will be provided.

The statistical analysis described above will be done on the Per Protocol Set and will be considered primary. The analyses will also be repeated for the Full Analysis Set.

No imputations will be performed for missing data.

Additional analyses may be performed as appropriate.

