- Percent and absolute change from baseline in biomarkers

Part 2

Primary:

• Percent change from baseline in muscle volume of injected muscle by MRI

Secondary:

- Percent and absolute change from baseline in intramuscular fat fraction of the injected muscle by MRI
- Percent change from baseline in strength measurements by maximum voluntary isometric contraction of ankle dorsiflexion measured by quantitative muscle testing
- Percent change from baseline in functional assessments: 10-meter walk/run, 6-minute walk test, Berg balance scale
- Percent and absolute change from baseline in CMTES2 and CMT-HI
- Presence and nature of AEs including injection site reactions and changes in clinical laboratory parameters
- Pharmacokinetic parameters for ACE-083 serum concentrations over time

Exploratory:

- Percent and absolute change from baseline in biomarkers
- Percent and absolute change from baseline in TA CMAP amplitude
- Percent and absolute change from baseline in gait parameters
- Activity level and falls (PamSysTM wearable device)
- Percent change from baseline in the 100-meter timed test

Methodology

This is a multicenter, phase 2 study to evaluate the safety, tolerability, pharmacodynamics (PD), efficacy, and PK of ACE-083 in patients with CMT1 and CMTX, to be conducted in two parts. Part 1 is non-randomized, open-label, dose-escalation and Part 2 is randomized, double-blind, and

placebo-controlled. Patients who have signed the informed consent form (ICF) and meet the eligibility criteria will be enrolled into the study.

Study Design

Part 1: N=Up to 18 (non-randomized, open-label, dose-escalation)

Cohort	ACE-083 Dose per Muscle ^a	ACE-083 n
1	150 mg	6
2	TBD up to 200 mg ^b	6
3	TBD up to 250 mg ^b	6

Part 2: N=Up to 40 (6-month, randomized, double-blind, placebo-controlled, with 6-month open-label extension)

	6-month placebo controlled		6-month open-label extension
ACE-083 Dose per Muscle ^a	ACE-083 n	Placebo n	ACE-083 n
TBD up to 250 mg ^b	20	20	40

^a Administered bilaterally by injection into the tibialis anterior muscle once every 3 weeks

^b Dose level to be based on recommendations from the Safety Review Team (SRT)

Part 1 (non-randomized, open-label, dose-escalation)

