5.2. Study Rationale

Hereditary motor sensory neuropathy (HMSN), also known as Charcot-Marie-Tooth (CMT) disease, is the most common form of hereditary neuropathy with a prevalence of 1 in 2500 individuals or about 125,000 people.⁶ A specific mutation in one of several myelin genes results in defects in myelin structure, maintenance, and formation. Duplication of the *PMP22* gene causes CMT1A, the most common type of CMT, accounting for approximately 40 percent of cases. X-linked forms of CMT are the second most common form of CMT and account for approximately 10 to 15 percent of cases.⁷

Patients with CMT typically present with both motor and sensory nerve manifestations, distal leg weakness, foot deformities (pes cavus, hammer toes), and sensory deficits. Involvement of the hands may also follow as the patient progresses. Weakness in the lower leg manifests as "foot drop" and patients have difficulty lifting their toes during ambulation. As this weakness progresses, patients begin to lose mobility and are at increased risk for falls and injury.

To date, treatment of CMT has been restricted to symptomatic interventions. Although some clinical and pharmacological trials have been performed, the results have not been encouraging.⁸ Patients will commonly wear braces and/or use assistive devices such as canes and walkers to preserve mobility but each of these orthopedic interventions is associated with practical as well as social limitations. Surgery has been shown to successfully treat deformities of the foot as well as foot drop but it is a more invasive option and not always an appropriate intervention in every case. In some patients, exercise is the recommended therapy but it is still uncertain whether exercise should be considered safe for the general CMT population and, if so, how the frequency, timing, and type of exercise should be selected for each patient.⁹

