##### Gait assessments

- General measures: Stride time (sec.), Stride length A (m), Stride length B (% height), Stride velocity A (m/s), Stride velocity B (height/s), Cadence (steps/min), Step length left (m), Step length right (m)
- Gait cycle phase measures: Swing left (%), Swing right (%), Stance left (%), Stance right (%), Double support initial right (%), Double support terminal left (%), Double support total (%)
- Gait assessment range of motion: Knee ROM left (deg.), Knee ROM right (deg.), Hip ROM left (deg.), Hip ROM right (deg.), Ankle ROM left (deg.), Ankle ROM right (deg.), Peak hip flexion angle in swing left (deg.), Peak hip flexion angle in swing right (deg.), Peak knee flexion angle in swing left (deg.), Peak knee flexion angle in swing right (deg.), Peak ankle flexion angle in swing left (deg.), Peak ankle flexion angle in swing right (deg.)
- Gait assessment foot drop: Mid-swing foot angle left (deg.), Mid-swing foot angle right (deg.)

For gait assessments reported on the left and right sides, the absolute and percent change from baseline will be determined for each side and then averaged. Should a patient have a gait assessment reported for one side (i.e. right side) but not the other side at an individual time point, the value for the average absolute (or percent) change from baseline for that patient and time point will be the absolute (or percent) change from the side from which the gait assessment was obtained.

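### Percent change, averaged over left and right, is planned for mid-swing foot angle and peak ankle flexion angle, where a baseline near or below zero would make it unstable or reverse its sign

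*SAP*

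**What the plan says.** The protocol synopsis lists "Percent and absolute change from baseline in gait parameters" among the exploratory endpoints.

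SAP 4.7.1.2 (Gait assessments) defines four groups of measures. Two contain angles in degrees: the foot-drop group, "Gait assessment foot drop: Mid-swing foot angle left (deg.), Mid-swing foot angle right (deg", and the range-of-motion group, which includes "Peak ankle flexion angle in swing left (deg.), Peak ankle flexion angle in swing right (deg" along with the hip and knee peaks. For measures recorded by side, "the absolute and percent change from baseline will be determined for each side and then averaged".

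SAP 4.7.2.2.1 (Gait) then plans the tables for all four groups, by cohort in Part 1 and by treatment group in Part 2: "Descriptive statistics of the raw data and change from baseline (percent and absolute change) will be provided for each type of measurement recorded". It adds: "Descriptive statistics for the average absolute and average percent change from baseline for the left and right sides will also be provided". SAP 4.7.2.2.2 (Gait) repeats this for the open-label extension, with Day 190 as the reference.

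The data-handling conventions in SAP 4.1.5 have no rule for a zero, near-zero or negative baseline. Neither document says which direction of an angle is positive.

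Two analyses avoid percent change. The only gait ANCOVA in the double-blind period, on mid-swing foot angle, uses absolute change. So does the gait comparison of open-label with double-blind in SAP 4.7.2.2.3.

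**The concern.** Percent change has a clear meaning only when zero means none of the quantity and baselines are positive. That is true of a stride time or a step length. It is not true of a foot or ankle angle measured from a reference position, which can fall on either side of zero.

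The trial makes low angles plausible. The protocol's rationale (5.2) describes foot drop and says "patients have difficulty lifting their toes during ambulation", and inclusion criterion 4 requires weak dorsiflexion (grade 3 to 4+).

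With a negative baseline, the formula gives an improvement a minus sign. With a small baseline of either sign, one side can dominate the left-right average, and one patient can dominate the group mean and SD. The tables for these variables could then show percent change and absolute change pointing in opposite directions, with nothing in the SAP to tell the reader which to believe.

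**Working it through.** The plan states no figure on this point to reproduce. The check is arithmetic on the SAP's rule, then a simulation under stated assumptions.

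**Rule.** For each side, percent change = 100 × (follow-up − baseline) / baseline. The patient's value is the mean of left and right.

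**One side, the same 5-degree gain throughout** (positive taken as dorsiflexion, an assumption):

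| Baseline (degrees) | Percent change |
|---|---|
| -10 | -50% |
| -1 | -500% |
| -0.5 | -1000% |
| 0 | undefined |
| +0.5 | +1000% |
| +1 | +500% |
| +10 | +50% |
| +30 | +16.7% |
| +60 | +8.3% |

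**Two sides.**
- Left -2 to +2: 100 × 4/(-2) = -200%. Right +4 to +8: 100 × 4/4 = +100%. The mean is (-200 + 100)/2 = -50%, although each side gained 4 degrees.
- Left -4 to +1: 100 × 5/(-4) = -125%. Right 10 to 15: 100 × 5/10 = +50%. The mean is -37.5%, for a 5-degree gain on each side.
- The mirror-image worsening, left -4 to -9 and right 10 to 5, gives +125% and -50%, a mean of +37.5%.

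**Two periods.** The open-label tables divide by the Day 190 value. A side going from -2 to +2 by Day 190 and then to +6 gains 4 degrees in each period, yet reads -200% in the first and 100 × 4/2 = +200% in the second.

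**How often the direction is wrong.** Assumed, because the documents give no values: a gain with mean 3 degrees and SD 2 on each side, a correlation of 0.6 between sides, and a baseline SD of 4 or 6 degrees. Among patients whose average absolute change is positive, the share whose averaged percent change is negative is:

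| Mean baseline (degrees) | Share shown as worse (range over the two SDs) |
|---|---|
| -5 | 77-87% |
| 0 | 50% |
| 5 | 13-23% |
| 10 | 1-7% |
| 15 | about 0.2-1.3% |
| 20 | about 0.2-0.3% |

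These shares hardly move if the 0.6 correlation is applied to the gains as well as to the baselines.

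**Spread.** At a mean baseline of 0, the 5th and 95th percentiles of the averaged percent change are about ±620% for a baseline SD of 4 and about ±410% for an SD of 6. A separate simulation used 20 patients per arm, a gain of exactly 5 degrees for everyone, a baseline SD of 5 and independent sides. The median within-arm SD was about 665 percentage points at a mean baseline of 0, against about 2 at a mean of 30.

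**The case against.** The strongest objection is that the key premise is not in the documents. They give names and units but no baseline angle, zero reference or sign convention. The presence of foot drop does not show that recorded angles reach zero. If mean baselines were 15 degrees or more, the wrong-direction share would be negligible. This stands, and it makes the size conditional. The rule itself is written down, however, and nothing in the SAP guards against the case.

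The second objection is scope. Range-of-motion measures are ranges and cannot be negative, and peak hip and knee flexion in swing are less likely to lie near zero. This also stands. A reader might infer that percent change is unsound for every gait angle, but that goes too far. The plausible problem is mid-swing foot angle and peak ankle flexion angle.

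The third objection is consequence. A reader might infer that the trial's foot-drop result could come out backwards. The documents do not support that. The mid-swing foot angle ANCOVA uses absolute change, as does the comparison of the two periods. Gait appears in neither the responder criteria (SAP 4.7.2.3) nor the subgroup parameters (4.9). Raw values and absolute changes are tabulated as well, so a careful reader would see the gain in degrees.

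A lighter remedy would be to omit percent change where baseline is zero or negative. That would remove patients on the basis of their baseline and keep the small positive baselines, where a 5-degree gain from 0.5 degrees still reads +1000%. Dividing by the absolute value of baseline repairs the sign but not this instability.

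**Conclusion.** The point holds in a limited form. For mid-swing foot angle and peak ankle flexion angle, the planned left-right averaged percent change can show improved patients as worse, and it can be dominated by a few baselines near zero.

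The reversal for a negative baseline is a matter of arithmetic. How often it would occur rests on assumed angles, an assumed sign convention and an assumed gain. Under those assumptions it ranges from most improved patients (mean baseline -5 degrees) to about 1% or fewer (15 degrees and above).

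The effect is confined to descriptive tables of an exploratory endpoint. No hypothesis test and no primary or secondary result depends on it. This is a minor point, worth correcting because the correction is nearly free.

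**What to change.** - In SAP 4.7.1.2, state the zero reference and sign convention for the foot and flexion angles. For mid-swing foot angle and the peak flexion angles (the ankle in particular), define raw values and absolute change only.
- Carry this into the gait text of SAP 4.7.2.1 (Part 1 motor function), 4.7.2.2.1 and 4.7.2.2.2.
- Keep percent change for times, lengths, velocities, cadence, gait-phase percentages and range of motion.
- Record the departure from the protocol's exploratory endpoint in SAP Section 5, which currently lists no change for gait.

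The cost is a few sentences and somewhat fewer tables. No information is lost, because raw values and absolute change remain and absolute change is already the scale of the SAP's gait model.

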### **Activity Level**

Individual data will be listed.

Exploratory analyses may be performed as appropriate.

No imputations will be performed for missing data.

#### **4.7.2.2.2. Open-Label Extension**

##### **Muscle Strength (MVIC)**

Individual data will be listed. The listing of such data will be collated with the data collected in the double-blind, placebo-controlled phase.

Descriptive statistics will be provided for raw data and changes (percent and absolute change) from the start of the open-label extension (Day 190) will be provided by treatment for each scheduled time for each side treated as well as the average from the left and right sides.

Additional analyses may be performed as appropriate.

##### **MRC-MMT Decimal Score**

Individual data will be listed. The listing of such data will be collated with the data collected in the double-blind, placebo-controlled phase.

Descriptive statistics will be provided for raw data and changes (percent and absolute change) from the start of the open-label extension (Day 190) will be provided by treatment for each scheduled time for each side treated as well as the average from the left and right sides.

Additional analyses may be performed as appropriate.

### **10-Meter Walk/Run Test**

Individual data will be listed. The listing of such data will be collated with the data collected in the double-blind, placebo-controlled phase.

For the time to complete the 10-meter walk/run, descriptive statistics will be provided for raw data and changes (percent and absolute change) from the start of the open-label extension (Day 190) will be provided by treatment for each scheduled time.

Additional analyses may be performed as appropriate.

### **6-Minute Walk Test**

Individual data will be listed. The listing of such data will be collated with the data collected in the double-blind, placebo-controlled phase.

For the cumulative distance recorded at 6 minutes, descriptive statistics will be provided for raw data and changes (percent and absolute change) from the start of the open-label extension (Day 190) will be provided by treatment for each scheduled time.

Additional analyses may be performed as appropriate.

### **Berg Balance**

Individual data will be listed. The listing of such data will be collated with the data collected in the double-blind, placebo-controlled phase.

Descriptive statistics will be provided for raw data and changes (absolute and percent change) from the start of the open-label extension (Day 190) will be provided by treatment for each scheduled time.

Additional analyses may be performed as appropriate.

### **Falls**

Individual data on the number and type of falls recorded in 4-week time intervals along with details on the timing and classification of the individual falls recorded, per day, type of assistance, and information related to input (whether the fall was recorded by device detection or recorded by the individual patient) will be provided in a listing. This data will be included with the data collected in the double-blind placebo-controlled phase.

The number of falls as well as the number of patients who fell at least once occurring from Week 25 up to Week 48 inclusive will be summarized by treatment, including separate summaries for subintervals as outlined in [Section 4.7.1.2](#). A record of “Near-fall” will not be counted as a “Fall”.

Additional analyses may be performed as appropriate.

**CMT-HI**

Individual data will be listed. The listing of such data will be collated with the data collected in the double-blind, placebo-controlled phase.

For the total CMT-HI and subgroup scores, descriptive statistics will be provided for raw data and absolute change from the start of the open-label extension (Day 190) will be provided by treatment for each scheduled time.

Additional analyses may be performed as appropriate.

**CMTES2**

Individual data will be listed. The listing of such data will be collated with the data collected in the double-blind, placebo-controlled phase.

For the CMTES2 score, descriptive statistics will be provided for raw data and absolute change from the start of the open-label extension (Day 190) will be provided by treatment for each scheduled time.

Additional analyses may be performed as appropriate.

**Gait**

Individual data will be listed. The listing of such data will be collated with the data collected in the double-blind, placebo-controlled phase.

For each type of measurement recorded (i.e. “General measures”, “Gait cycle phase measures”, “Gait assessment range of motion”, and “Gait assessment foot drop”), descriptive statistics will be provided for raw data as well as absolute and percent changes from the start of the open-label extension (Day 190) will be provided by treatment for each scheduled time. Descriptive statistics of the average absolute and average percent change from baseline for the left and right sides will also be provided.

Additional analyses may be performed as appropriate.

**Activity Level**

Individual data will be listed.

Exploratory analyses may be performed as appropriate.

No imputations will be performed for missing data.

